Surgical cases requiring sedation by an anesthesia provider, also known as monitored anesthesia care (MAC), are a popular choice for outpatient surgical procedures with benefits of “less physiologic disturbance and a more rapid recovery than general anesthesia” (Das 2015). However, MAC cases still come with risk: per the American Society of Anesthesiologists closed claim database, “the most common malpractice claim is inadequate oxygenation/ventilation, with more than 80% of claims of this nature resulting in brain damage or death” (McMurray 2020). Since 1908, anesthesia providers have been utilizing interventional airway devices that manipulate the soft tissues of the nasopharynx, oropharynx, and hypopharynx to relieve obstruction to support patient ventilation and oxygenation; however, there are few studies that directly compare the efficacy & side effect profiles between these devices (Matioc 2019). Additionally, a recent survey indicates that many anesthesia providers desire an alternative airway intervention device than the current ones most commonly used in current practice (McMurray 2020). We will examine the possibility of using at-home, over-the-counter anti-snoring devices as an intraoperative airway device.

STUDY ENDPOINTS:

PRIMARY ENDPOINT: Combined total number of airway interventions during an anesthetic sedation case – including head tilt/rotation, mandible thrust, chin lift, shoulder lift, neck extension or flexion, tongue pull.

SECONDARY ENDPOINTS:

- Satisfaction of Anesthetist via survey
- Maximum/minimum end-tidal CO₂
- # of times SpO₂ value < 92%
- % of time during the case SpO₂ < 92%
- maximum/minimum SpO₂ value
- EKG analysis that were not recorded as “Normal Sinus rhythm”:
- Heart rate maximum & minimum
- maximum/minimum Systolic, diastolic, and mean blood pressure
- Total dose and type of hypnotic & narcotic given
- Case type
- Case duration
- Baseline characteristics (Age, Gender, BMI)

- Time spent in Phase 2 PACU Recovery
- Adverse events (i.e. regurgitation and aspiration, bronchospasm, cough, case converted to GA)

STUDY INTERVENTION(S) / INVESTIGATIONAL AGENT(S):

We will use anti-snoring appliance devices (specifically the FDA approved Zyppah) to attempt to relieve tissue obstructions that cause snoring during sleep. The application of the devices to the body is less invasive than other common intraoperative rescue airway devices (e.g. nasal trumpets and oral airways) which are not designed to be patient specific.

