We will be purchasing the device from the manufacturer's website. We will be purchasing the devices via funds awarded by the James E. Eckenhoff Residents' Research Award.

The device will be stored in the PI's key-locked office, until it is given to a research team member to be given to a subject after recruitment and prior to their procedure. Research personnel will bring the appliance to the preoperative holding area & will help mold it for the patient, and will insert it prior to transport to the operating suite. The device will remain in place until the completion of procedure, unless the anesthesia provider in the room feels it needs to be removed for any reason. The patient or anesthesia personnel can remove the device at their leisure after completion of the procedure.

PROCEDURES INVOLVED:

The study participants will be recruited into two groups: patients wearing an anti-snoring appliance device during an anesthetic sedation procedure; and those who do not wear an anti-snoring device. To ensure anesthetic providers have easy access to the patient's airway for standard of care manipulation (if needed), the patients eligible for this study would be those who are undergoing procedures below the umbilicus (e.g. gynecological, urological, orthopedic, etc.) in addition to having a STOP-BANG score of 2 or greater. This will ensure patient safety and provide a wide demographic of potential subjects to increase the generalizability of the study.

For both patient groups, the study procedure is the same. Eligible patients will be identified by chart review of various elements of the electronic medical record, as follows:

Patients will be identified and be seen by the study team in the pre-operative clinic on 17th floor Lavin and in the holding area to interview individuals who are to undergo eligible anesthetic sedation procedures as above. If the patient agrees to participate in the study, they will be randomized at that time to one of the two groups (anti-snoring appliance device to be used for procedure or not).

The groups in the prospective, randomized, controlled trial in patients undergoing anesthetic sedation procedures will be as follows:

Group #1: Anti-snoring appliance (Zyppah) that will be utilized during their procedure
Group #2: Control group, that will not utilize anti-snoring appliance

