Participants will be randomized to treatment groups based on a random computer-generated (<https://www.randomizer.org>). Anesthesia providers will not be blinded to randomization, and research personnel will observe the procedure to collect all outcome measures in this study.

For group 1, the study team will aid them in molding and preparing the device in the pre-operative area. Anesthesia providers will be instructed on how the device works and when to place it (with aid from the research team) in addition to receiving a question and answer sheet and protocol they can follow to take with them to the operating room. Prior to the administration of anesthetic medications, the patient will be aided in inserting the device, and wear it throughout the entirety of the case. Regardless of the group, from the start of sedation until the patient leaves the procedure suite. When an anesthesia provider believes they make a clinically significant airway intervention (either via jaw lift, head turning, etc.) they will be instructed to use the “mark now” icon in the anesthetic record and utilize the free text to indicate what intervention was done and why.

All standard practices and standard monitors for anesthetic sedation cases will be utilized.

A post-survey will be administered to anesthesia providers in group 1 to gauge satisfaction.

Anesthetic record will be reviewed by research team members following the end of the case.

DATA AND SPECIMEN BANKING

We will collect data including reason for procedure, type of procedure, and patient demographics (including medical history, sex, age, and weight); in addition to data collected via electronic chart review including: Documented Obstructive Sleep Apnea (OSA), date of procedure, surgical case length, anesthesia type requested, anesthesia type documented, Provider team staff composition, documented neuraxial or nerve block procedure (if applicable), “in room” time, max/min heart rate, min/max oxygen saturation, number of instance oxygen saturation fell below 92%, % of time during case where oxygen saturation was below 92%, min/max end tidal CO₂, min/max blood pressure, total dose of hypnotic & narcotic given, “out of room” time, adverse events noted in charting, free-text written by providers, and total hospital length of stay.

SHARING RESULTS WITH PARTICIPANTS

Results will not be shared with participants.

STUDY TIMELINES

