Patients can withdraw from the study at any time and their data will be deleted, and in no way will this impact their care since the study explicitly does not affect the standard of care. The study team will notify the PI by secure NM or NU email if a subject withdraws from the study.

RISKS TO PARTICIPANTS

No significant risk to the patient exists with the utilization of an anti-snoring device. The devices are non-invasive and can be easily removed by the patient or anesthesia provider, if needed. There is the potential for damage to loose teeth, gums or tongue since this is a moldable mouth guard. There is the potential for loss of confidentiality even with strict measures in place to prevent occurrence.

POTENTIAL BENEFITS TO PARTICIPANTS

If functional, the participants may benefit from utilization of an anti-snoring device by reducing snoring and airway obstruction; which would lead to improved sleep and less fatigue. It may also prevent the use of more invasive rescue airway devices that can cause patient discomfort including damage to the lips, teeth, gums, tongue, naso- and oropharynx.

DATA MANAGEMENT AND CONFIDENTIALITY

Data Statistics:

Preparation: In previous studies looking at patient satisfaction for snoring relief, 570 participants were analyzed with one of the anti-snoring devices resulting in a statistically significant benefit. However, there are currently no large published studies that analyze the use of an anti-snoring devices in the setting of MAC anesthesia. Additionally, there are no large studies comparing the efficacy of traditional invasive airway rescue devices (e.g. oral/nasal airways).

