We utilized a study by Qiansong Xiao et al titled “Comparison of Nasopharyngeal Airway Device and Nasal Oxygen Tube in Obese Patients Undergoing Intravenous Anesthesia for Gastroscopy: A Prospective and Randomized Study”, which compared the oxygen saturation levels in patients who did or did not have an invasive nasopharyngeal airway at the beginning of the anesthetic sedation procedure, to perform our power analysis. 260 patients were included and randomized; with 3 patients excluded due to failure of the nasopharyngeal airway. Based on the differences in “change in SpO₂” and “raising the mandible” between their test and control groups, and power analysis was completed with an alpha value of 0.05 and power value of 80%. The n per group that was calculated to provide the appropriate power to identify a statistical difference was 12 patients per study group. To compensate for patients in our study being less obese we increased the number per group to 14 subjects. We plan to approach 28 subjects and randomize 28 patients to 2 groups, allowing for patients who may not end up getting their procedure or instances where data collection is incomplete or absent.

Statistical analysis: Data will be compared between all groups using paired t-test with p< 0.05 required to reject the null hypothesis.

Data Security:

All collected data will be stored in REDcap using NM password protected computers for data entry. Data in REDcap is backed up nightly using NM servers which are only accessible to the NM IT administrator. Paper documents generated during the study will be stored in Arkes Pavilion 10th floor Department of Anesthesiology locked research cabinet. Data both paper and electronic will be destroyed 5 years after the completion of the study using current department policy and approved vendors.

PROVISIONS TO MONITOR THE DATA TO ENSURE THE SAFETY OF PARTICIPANTS N/A

PROVISIONS TO PROTECT THE PRIVACY INTERESTS OF PARTICIPANTS

Patients in this study undergoing a procedure under anesthetic sedation can be stressful. If a subject does not feel comfortable with participating, they will have the option to opt out at any time and it will not impact their care if they choose to do so.

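### The only test named is a paired t-test, but the two groups are independently randomised and unpaired, so the primary p-value is not uniquely defined

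*Combined protocol and SAP*

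**What the plan says.** The analysis plan is one sentence under Data Management and Confidentiality, Data Statistics: "Data will be compared between all groups using paired t-test with p< 0.05 required to reject the null hypothesis". No other test is named anywhere in the document.

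The design is set out in Procedures Involved. Once patients agree to take part, "they will be randomized at that time to one of the two groups". The comparator consists of different people: "Group #2: Control group, that will not utilize anti-snoring appliance". Allocation is described only briefly: "Participants will be randomized to treatment groups based on a random computer-generated", with an online randomiser cited and no mention of blocks, strata or matched pairs.

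Study Endpoints defines the primary endpoint as "Combined total number of airway interventions during an anesthetic sedation case", which is one number per patient. The secondary list includes categorical items such as rhythms other than normal sinus and adverse events.

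Losses are foreseen. Data Statistics plans 14 per group, 28 in all, "allowing for patients who may not end up getting their procedure or instances where data collection is incomplete or absent". Withdrawal of Participants adds: "Patients can withdraw from the study at any time and their data will be deleted".

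**The concern.** A paired t-test works on within-pair differences. It needs a one-to-one link between each device patient and one control patient, and therefore equal arms. Neither is provided for.

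Three things follow if the sentence is applied literally:

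- The analyst has to make up a pairing. The mean difference is the same under every complete pairing, but the standard deviation of the differences is not, so the p-value depends on an arbitrary choice.
- Nothing requires that choice to be made before outcomes are known.
- If the arms end unequal, patients without a partner drop out of the analysis, which matters in a trial of 28.

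A t-test of either kind also does not suit the categorical secondary endpoints. At stake is whether the trial has a defined primary analysis.

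**Working it through.** **1. Is there any source of pairs?** The whole document was searched for features that could justify a paired test: matched or pair-wise randomisation, crossover, a second procedure in the same patient, or a baseline value of the primary count. None appears. The test and the design do not fit each other.

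**2. The plan's own figure.** Inputs from Data Statistics: alpha 0.05, power 80%, 12 per group, raised to 14. No effect size, standard deviation, event rate or sidedness is given, so the 12 cannot be reproduced. It can only be back-solved, assuming two-sided alpha:

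- Independent t-test, noncentrality d·√(n/2), 2n − 2 df: 80% power at n = 12 needs d = 1.197.
- Paired t-test with unrelated pairs, same noncentrality, n − 1 df: 80% power at n = 12 needs d = 1.257.

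| Assumed d | n per group | Independent | Paired | Loss (points) |
|---|---|---|---|---|
| 1.197 | 12 | 80.0% | 76.1% | 3.9 |
| 1.197 | 14 | 86.2% | 83.3% | 2.9 |
| 1.257 | 12 | 83.7% | 80.0% | 3.7 |
| 1.257 | 14 | 89.3% | 86.7% | 2.6 |

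The loss comes from halving the degrees of freedom: at 14 per group the critical t is 2.056 on 26 df and 2.160 on 13 df.

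**3. One data set, many answers.** Assumed counts, not from the documents:

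- Device: 0,0,1,1,1,2,2,2,2,3,3,4,4,5 (sum 30, mean 2.14, SD 1.51).
- Control: 0,1,1,2,2,3,3,4,4,4,5,6,7,8 (sum 50, mean 3.57, SD 2.34).

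The mean difference is 20/14 = 1.43.

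- Independent test: standard error √[(1.51² + 2.34²)/14] ≈ 0.745, t ≈ 1.92 on 26 df, p = 0.066 (Welch 0.068).
- Paired, both arms sorted ascending: the differences have sum of squares 40, variance (40 − 20²/14)/13 = 0.879, t ≈ 5.70 on 13 df, p = 0.00007.
- Paired, one arm reversed: sum of squares 218, variance (218 − 20²/14)/13 = 14.57, t ≈ 1.40, p = 0.185.
- 100,000 random pairings (of 14! ≈ 8.7 × 10¹⁰): median p 0.078, central 95% from 0.019 to 0.139, with 21.8% below 0.05.

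**4. How often this matters.** Simulation of 3,000 trials with 200 random pairings each, 14 per arm, in ten assumed Poisson or negative-binomial scenarios (five with no true difference):

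- One outcome-blind pairing, no true difference: rejects in 4.1% to 5.2% of trials (two-sample t-test 4.5% to 5.6%).
- Two outcome-blind pairings give opposite verdicts in 3.0% to 11.5% of trials.
- The verdict is not unanimous over the 200 pairings in 20% to 51% of trials.
- With no true difference, at least one of the 200 pairings rejects in 21.7% to 23.1% of trials.

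The first two lines describe a pairing fixed honestly. The last two describe the room for choice if pairings are tried after the data are seen. In a separate run with normal data, sorting both arms by outcome before pairing, the extreme case, gave a type I error of 54.5%.

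**5. Unequal arms.** Both figures are conditional:

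- If randomisation of 28 is simple and unblocked: P(14/14) = C(28,14)/2²⁸ = 0.149, and the mean gap between arms is 28 × 0.149 ≈ 4.2 patients.
- If 14/14 is forced and four patients are lost at random: P(two from each arm) = C(14,2)²/C(28,4) = 8281/20475 = 0.404, so the arms are unequal with probability 0.596.

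**The case against.** The strongest reply is that the word paired is a slip. The sentence speaks of comparing groups, the sample size is expressed per group, and the power calculation draws on differences between the test and control arms of another randomised trial. On that reading the intended test is a two-sample t-test and none of the pairing problems arise. This is plausible, but nothing in the documents confirms it, and the sentence is the entire analysis plan. Either reading calls for the same correction.

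Second, the large figures describe a search over pairings, on assumed counts. That is right: for an outcome-blind pairing the effects are small, and those figures should carry the weight.

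Third, the unequal-arm figures are hypothetical. Simple randomisation is an assumption and fits poorly with a target of 14 per group. The illustration of four losses uses the 28 and 24 in the Participant Population(s) table, but 24 may be the number needed (2 × 12) rather than expected completers, and the local row reads 28 and 28. This stands. The documents support the possibility of losses but give no rate. The defect does not depend on either figure.

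Fourth, the categorical endpoints are secondary and Fisher's exact test is one choice among several. That is fair on importance, but those endpoints still have no usable test.

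**Conclusion.** The concern holds and must be fixed. That the named test does not fit the design is certain from the text and rests on no assumption. The consequence is an undefined primary analysis: the same 28 values can give p-values on either side of 0.05 depending on an unspecified pairing.

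The size depends on conduct. With a pairing fixed blind to outcome, type I error stays near 5% and the power loss is about 3 to 4 points, under effect sizes back-solved from 12 per group. With pairings tried after the fact, the chance of finding at least one nominally significant result under no effect rose to about 22% over 200 tries in the assumed scenarios. No claim is made that the trial falls below 80% power, since the documents give no effect size from which to show it.

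**What to change.** In Data Statistics, replace the paired t-test with one prespecified independent-groups comparison of the primary count that uses all patients with data. A Welch two-sample t-test, a rank-sum test or a permutation test would each serve. The choice is the investigator's, but a single test must be named before any outcome data are examined. Name a test for categorical endpoints such as rhythm and adverse events; Fisher's exact test suits arms of this size. While editing, state which kind of test the 12 per group was calculated for.

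The cost is a sentence or two in the statistical section, with no added patients, data or procedures.

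### Even without the word 'paired', one t-test for all data cannot be run on case type or drug type, suits the yes/no items poorly, and may lose power on the SpO₂ < 92% endpoints

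*Combined protocol and SAP*

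**What the plan says.** The only analysis method is in the Statistical analysis paragraph under Data Management and Confidentiality: "Data will be compared between all groups using paired t-test with p< 0.05 required to reject the null hypothesis". No endpoint is exempted and no second method is named.

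The Study Endpoints section lists very different kinds of data:

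- Primary, a count per patient: "Combined total number of airway interventions during an anesthetic sedation case".
- Desaturation: the number of SpO₂ values under 92%, and the percentage "of time during the case SpO₂ < 92"%.
- Part numeric, part nominal: "Total dose and type of hypnotic & narcotic given".
- Nominal: case type.
- Yes/no or categorical: EKG findings other than normal sinus rhythm, and adverse events.
- Continuous: heart rate, blood pressure, end-tidal CO₂, minimum and maximum SpO₂, drug dose and durations.

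On size, the calculated number "was 12 patients per study group", and then "we increased the number per group to 14 subjects", or 28 in total.

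**The concern.** A t-test compares two means. Applied to every listed endpoint, it meets three different problems: data with no mean (case type, drug type), rare yes/no events where it gives little usable information, and outcomes that may be mostly zero with a long right tail, where one or two extreme patients can dominate the result.

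For some listed endpoints the plan therefore cannot be followed, and a method would have to be chosen once the data are in hand. Providers are not blinded, and nothing says that the analyst is. The desaturation endpoints matter beyond their secondary status, because change in SpO₂ was one of the two quantities used to set the sample size.

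**Working it through.** **The plan's own figure.** The 12 per group cannot be reproduced, because no difference, SD or rate is given. It can only be solved backwards. For an independent-groups t-test at two-sided 5% and 80% power, n ≈ 2(1.96 + 0.84)²/d² + 1.96²/4. With d = 1.20 this is 15.68/1.44 + 0.96 = 11.9, so 12 implies a standardised difference of about 1.2. This says nothing about the shape of any endpoint, so every distribution below is an assumption.

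**Nominal endpoints.** No distribution is needed here. Take three case types and 14 patients per arm, as an invented example. One arm has 7 gynecological and 7 orthopedic cases; the other has 14 urological cases.

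- Coded gynecological = 1, urological = 2, orthopedic = 3, the means are (7×1 + 7×3)/14 = 2 and 14×2/14 = 2, a difference of 0.
- Coded gynecological = 1, orthopedic = 2, urological = 3, they are (7×1 + 7×2)/14 = 1.5 and 3, a difference of 1.5.

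The result depends on arbitrary labels. The same holds for drug type.

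**Yes/no items.** Exact enumeration at 14 per group, for event rates from 5% to 50%, gives a t-test error rate of at most 5.2%, so false positives are not the problem. The problem is what it reports when events are rare. With 0 of 14 in both arms the standard error is 0 and the statistic is undefined. An exact 95% interval for 0 of 14 still gives an upper limit of 1 − 0.025^(1/14) = 23%.

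**Percent of time SpO₂ < 92%.** Simulated at 14 per group, two-sided 5%, as (any desaturation: yes/no) × (severity: gamma or lognormal). Tests are the independent-groups t-test and the rank-sum test.

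| Assumed effect | t-test power | Rank-sum power |
|---|---|---|
| Any desaturation 60% v 20%, same severity | 17–48% | 54–56% |
| Any desaturation 50% v 15%, same severity | 16–43% | about 48% |
| Any desaturation 70% v 30%, same severity | 18–44% | about 50% |
| 60% in both arms, severity ×0.2, log-SD 0.5 | 81% | 38% |
| 60% in both arms, severity ×0.2, log-SD 1.0 | 41% | 24% |
| 60% v 40%, severity ×0.4, log-SD 0.5 | 68% | 49% |
| 60% v 40%, severity ×0.4, log-SD 1.0 | 33% | 34% |

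The first three rows span several severity distributions. The gap is smallest with mild skew and largest with strong skew. The order reverses when the appliance mainly shortens desaturation and skew is mild or moderate.

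**Number of falls below 92%.** With negative binomial counts (k = 0.2–0.5), t-test power is 12–70% and rank-sum 19–74%, a loss of 4 to 13 points.

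**Primary count.** The independent-groups t-test against the same test on square-root counts:

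| Assumed counts | t-test | Square-root scale |
|---|---|---|
| Poisson, 2 v 1 | 55% | 54% |
| Poisson, 4 v 2 | 84% | 83% |
| Negative binomial k = 2, 3 v 1 | 73% | 73% |
| Negative binomial k = 1, 3 v 1 | 50% | 53% |
| Negative binomial k = 0.5, 2 v 1 | 14% | 16% |

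Across scenarios with k = 0.5–0.7 the gain is about 2 to 7 points. Against the rank-sum test the t-test is equal or slightly better (Poisson 2 v 1: 55% v 52%; k = 0.5, 2 v 0.7: 24% v 24%).

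**The case against.** The strongest reply is that the desaturation comparison depends on which effect is assumed. If the appliance changes only whether a patient desaturates, the rank test is favoured; an effect on length is just as plausible, and then the t-test can be much better. No share of zeros is documented. Sleep apnea, COPD and asthma are excluded, so desaturation may be rare: at 20% v 5%, rank-sum power is only 16%. This stands, and it makes the power argument conditional.

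A second reply is that case type is really a descriptor and that the protocol's null hypothesis concerns airway maneuvers. That lowers the stakes. It does not remove the problem, because case type and drug type are listed as secondary endpoints and the analysis sentence makes no exception.

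A reader might also infer that the t-test wastes power on the count primary. The documents do not support this: they give no mean, SD or dispersion, and a gain from another scale appears only under strong overdispersion and is small. Nor does the plan inflate error for yes/no items, as the enumeration shows.

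**Conclusion.** The point holds in limited form and should be fixed before analysis.

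- **Certain, with no assumption:** the stated test cannot be applied to case type or drug type, and it is a poor choice for EKG findings and adverse events.
- **Conditional:** on percent of time SpO₂ < 92% the t-test gives up roughly 6 points (48% v 54%) to 39 points (56% v 17%) if the appliance acts on whether patients desaturate, at an assumed 60% v 20%. The loss on the number of falls is smaller. The order can reverse if it acts mainly on length.
- **Not supported:** a material power loss on the primary. Replacing the primary test on that ground would be a preference, not a correction.

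**What to change.** Replace the analysis sentence with independent-groups methods by data type:

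- **Primary count and continuous measures** (heart rate, blood pressure, end-tidal CO₂, minimum and maximum SpO₂, drug dose, durations): independent-groups t-test.
- **Number of falls and percent of time SpO₂ < 92%:** Wilcoxon rank-sum test. Also report by arm the share of patients with any fall below 92%, and the mean difference, so that an effect on length remains visible.
- **Case type and drug type:** n (%) by arm.
- **EKG findings and adverse events:** n (%) by arm, with exact confidence limits or Fisher's exact test.

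The cost is a few lines in the Statistical analysis paragraph, with no new data or patients. The one downside is that the rank test is less powerful than the t-test if the appliance mainly shortens desaturation.

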Individual subjects and anesthetic providers will participate in the study for the duration of their procedure requiring anesthetic sedation. It will take approximately 3 months to enroll participants and approximately 3 months to perform data analysis.

INCLUSION AND EXCLUSION CRITERIA

Inclusion criteria

Adult patients (age 18-89 years old)

Undergoing procedures below the umbilicus requiring anesthetic sedation without an invasive airway

STOP-BANG score of 2 or greater.

English or Spanish language speaking

Exclusion criteria

Patients requiring general anesthesia.

Sleep apnea

Serious breathing or respiratory disorders such as COPD, asthma, emphysema

Poor dental health including severe gum disease, loose teeth, abscess, mouth sores, bleeding gums

Dental implant place within last 3 months

TMJ disorder

Mouth or jaw pain

Full dentures

Wear braces

Sleep with CPAP or other devices

Other special populations (individuals who are not yet adults, prisoners, vulnerable populations, pregnant) will also be excluded.

VULNERABLE POPULATIONS:

Will not be a part of study.

PARTICIPANT POPULATION(S)

Accrual Number:	Category/Group: (Adults/Children Special/Vulnerable Populations)	Consented: Maximum Number to be Consented or Reviewed/Collected/Screened	Enrolled: Number to Complete the Study or Needed to Address the Research Question
Local	Adults	28	28
Study-wide		28	24
Total:		28	24

RECRUITMENT METHODS

Patients undergoing an eligible procedure requiring anesthetic sedation will be identified by the anesthesiology team by chart review and the schedule in the pre-operative clinic on the 17th floor Lavin pavilion prior to their procedure. They may also be approached by the research team the morning of their procedure for possible enrollment into the study. If the potential subject is interested in the study a study team member will ask for the subject's email address to send an Econsent using REDCap for their review.

The source of participants will be NMH pavilions (Galter, Feinberg, Lavin) in addition to Prentice Women's Hospital.

COMPENSATION FOR PARTICIPATION IN RESEARCH ACTIVITIES

There will be no compensation for participation; however, patients who are randomized into one of the anti-snoring device groups will be allowed to keep the device, if they wish.

WITHDRAWAL OF PARTICIPANTS

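### Baseline BMI is collected but left out of the only planned comparison, which may cost precision in a 14 v 14 trial; this is not a bias, and the paired test has to be replaced first.

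*Combined protocol and SAP*

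**What the plan says.** The primary endpoint (Study Endpoints) is a count per patient: "Combined total number of airway interventions during an anesthetic sedation case". The analysis is given under Data Management and Confidentiality, Statistical analysis: "Data will be compared between all groups using paired t-test with p< 0.05 required to reject the null hypothesis". No covariate, stratified analysis or other use of baseline data is mentioned.

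Procedures Involved describes computer-generated allocation to two groups, with no stratification, blocking or minimisation.

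BMI is available. It appears, placed among the secondary endpoints, under "Baseline characteristics (Age, Gender, BMI". STOP-BANG is also known before randomisation, because eligibility requires a "STOP-BANG score of 2 or greater". However, it is not in the list of data to be collected under Data and Specimen Banking.

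The sample-size text (Data Statistics) links obesity to the expected result. It obtains 12 per group and then says: "To compensate for patients in our study being less obese we increased the number per group to 14 subjects". The total follows: "We plan to approach 28 subjects and randomize 28 patients to 2 groups".

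**The concern.** The plan changes its sample size because its patients are less obese than those in the source trial, and then does not use BMI in the analysis. If BMI predicts how many interventions a patient needs, two things follow in a trial of 28.

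- Variation that BMI could explain stays in the error term, so the interval for the device effect is wider than it need be.
- With no stratification, the arms can differ in BMI by chance. An unadjusted estimate then carries the part of the difference that BMI would account for.

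The stake is a few points of power and a somewhat wider interval, recoverable without more patients or more data. Any covariate has to be named in advance, because picking one after seeing an imbalance would be a data-driven choice.

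**Working it through.** **Inputs from the documents.** 14 per group (28 in total); alpha 0.05; 80% power; 12 per group as calculated before the increase.

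**Assumptions.** Two-sided test (sidedness is not stated); approximately normal outcome; independent groups; a linear model with one covariate. The documents give no effect size, no SD and no correlation *r* between BMI and the count, so *r* is varied from 0 to 0.5.

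**1. The plan's own figure.** The 12 per group cannot be reproduced forward, since no mean difference, SD or proportions are stated. Solving backwards with a two-sided unpaired t-test, 80% power at 12 per group implies a standardised difference of d = 1.197, about 1.20. At 14 per group the same calculation gives d = 1.10.

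**2. Unadjusted benchmark at 14 per group.** The standard error of the difference, in SD units, is √(2/14) = 0.378, with 26 degrees of freedom.
- d = 1.10: noncentrality 1.10/0.378 = 2.91, power 80%.
- d = 1.197: noncentrality 1.197/0.378 = 3.17, power 86%.

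**3. Adjustment for one covariate.** The variance is multiplied by (1 − r²) × (1 + k/(N − k − 3)). With k = 1 and N = 28 this is (1 − r²) × (1 + 1/24) = 1.0417 × (1 − r²), with 25 degrees of freedom. Break-even for the variance is r² = 1 − 1/1.0417 = 0.04, so r = 0.2.

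| r | Variance factor | Change in CI width | Power, d = 1.10 (unadjusted 80%) | Power, d = 1.197 (unadjusted 86%) |
|---|---|---|---|---|
| 0 | 1.042 | about +2% | 78% | 85% |
| 0.2 | 1.000 | about 0 | 80% | 86% |
| 0.3 | 0.948 | about −2% | 82% | 88% |
| 0.4 | 0.875 | about −6% | 85% | 90% |
| 0.5 | 0.781 | about −11% | 89% | 93% |

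Simulation with 20,000 trials per setting agrees with the power columns to within about half a point. Type I error stays near 5% both with and without adjustment.

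**4. Chance imbalance.** The standardised BMI difference between arms has standard error 0.378. The probability that it exceeds 0.5 SD in either direction is 2 × (1 − Φ(0.5/0.378)) = 18.6%, about 19%. An imbalance of 0.5 SD moves the unadjusted estimate by r × 0.5: 0.15 SD of the outcome at r = 0.3, and 0.25 SD at r = 0.5.

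**5. Why one covariate.** With two covariates the break-even rises to r² = 0.08. If neither is related to the count, power at d = 1.197 falls from 86% to 83%, against 85% with one.

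**The case against.** The strongest reply is that an unadjusted comparison of randomised arms is legitimate. It is unbiased over repeated randomisations, and its p-value and interval already allow for chance imbalance. That stands. A reader might infer from the 19% figure that the planned result would be biased or its type I error inflated. Neither follows, and the simulation shows no inflation.

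Second, the gain is conditional. The sentence on obesity compares this population with the source trial's. It bears on the expected result, and does not say that BMI predicts the count within an arm, which is what adjustment needs. Excluding sleep apnea and CPAP users while requiring a minimum STOP-BANG score may also narrow the range of airway risk and weaken any correlation. This stands too: below r of about 0.2 adjustment does not help, and the 0.3 to 0.5 range is an assumption.

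Third, a reader might infer that the trial also treats STOP-BANG as a driver of obstruction. The documents do not support this. Procedures Involved justifies the eligibility rule by safety and generalisability.

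Fourth, the paired test is the more serious fault in the quoted sentence, and the comparisons above use an unpaired test that the plan does not contain. This is correct, so adjustment makes sense only once the paired test is replaced. The endpoint is also a count, so the normal-outcome figures are illustrative.

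What remains is a cheap change with an uneven trade: at d = 1.10, about 2 points of power lost at worst, against about 2 to 9 points gained at correlations of 0.3 to 0.5.

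**Conclusion.** The point holds as an efficiency improvement, not as a validity error. The plan has one unadjusted comparison, no described stratification, and a collected baseline variable that it considers relevant enough to cite when changing its sample size. Leaving BMI out may lose precision; the documents do not show that it does.

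At the effect giving 80% unadjusted power, adjustment changes power by between about −2 and +9 points as the correlation goes from 0 to 0.5. At the larger effect implied by the plan's 12 per group, the change is from about −1 or −2 to +7 points (86% to 85% at correlation 0, 93% at 0.5). These figures rest on a normal outcome, a two-sided test, full data on 14 per arm and an assumed correlation. If only 12 per arm are analysed, break-even moves slightly, to r² of about 0.048 (r about 0.22).

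**What to change.** Rewrite the analysis sentence so that the primary comparison is an unpaired between-group model for the intervention count, with terms for group and continuous baseline BMI, for example a linear ANCOVA. State that BMI is fixed in advance as the only patient covariate, since 28 patients do not support a longer list. Report the unadjusted unpaired comparison as a sensitivity analysis. If a count model is preferred to the linear one, name it in advance; the power figures above apply to the linear version. Move BMI from the secondary endpoints to a list of baseline variables.

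The cost is a sentence or two of text, one degree of freedom, and about 1 to 2 points of power if BMI turns out to be unrelated to the count. No extra patients or data are needed.
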